##### **5.8.1 Patient Discontinuation**

Patients will be discontinued from further study drug administration in the event of any of the following:

- Intolerable toxicity as determined by the Investigator
- Progression of disease requiring an alternate therapy, in the opinion of Investigator
- Entry into another therapeutic clinical study or start of new anticancer therapy
- Significant deviation from the protocol or eligibility criteria, in the opinion of the medical monitor or Investigator
- Noncompliance with study or follow-up procedures

- Pregnancy
- Patient withdrawal of consent or decision to discontinue participation
- Termination of the study by the Sponsor
- Any other reason that, in the opinion of the Investigator, would justify removal of the patient from the study

In the event that a patient is withdrawn from the study, every effort must be made by the Investigator to document and report the reasons for withdrawal as thoroughly as possible. The reason(s) for withdrawal must be clearly reported on the appropriate page of the patient's eCRF. An eCRF must be completed for any patient enrolled, and an End-of-Treatment reason must be recorded for any patient who is enrolled, regardless of whether they receive study drug.

If a patient is discontinued from the trial for any reason, every effort must be made to perform all End-of-Treatment and 30 Days After Last Dose assessments per the schedule of events. In the event that the patient fails to return for the necessary visit(s), an effort must be made to contact the patient to determine the reason, and this information should be recorded in the appropriate source record and reported as a deviation.

All patients who permanently discontinue the study drug will be followed for survival. For patients who discontinue the study treatment due to a reason other than documented progressive disease (PD), additional tumor assessments should be documented, if available, until disease progression or start of another systemic anti-cancer therapy.

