## 3. EXPERIMENTAL PLAN

### 3.1 Study Design

This is a Phase 1/2, open-label, multicenter trial to evaluate the safety, pharmacokinetics, and anti-tumor activity of THE-630 in patients with advanced GIST. The study will be conducted in two parts: a dose escalation phase (Phase 1) and a subsequent expansion phase (Phase 2).

Phase 1 will employ a sequential dose escalation of oral THE-630 following a standard 3+3 design. Each cohort will have a minimum of 3 patients enrolled and followed for 28 days. Dose-escalation meetings will occur after all patients in the current cohort have either completed at least 28 days of observation after their first dose of THE-630 or have experienced a DLT. If no patients experience a DLT in the additional 3 patients (i.e., for a total of  $\leq 1$  of 6 patients with a DLT), dose escalation will continue until the MTD is identified. The RP2D is the MTD or less.

Upon identification of the RP2D, the expansion phase (Phase 2) will enroll 3 cohorts of patients with unresectable or metastatic GIST, with eligibility defined by prior therapy, as outlined within [Section 4.1](#). Patients will continue with the study treatment until progression of disease as determined by the Investigator, unacceptable toxicity, death, or consent withdrawal.

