### **6.3.7 Cycle 2 Day 28 and Day 28 of All Even Cycles Through Cycle 12 and every 3 Cycles Thereafter**

The following evaluations and procedures will be performed during this visit ( $\pm 3$  days):

- Disease assessment by CT scan and MRI (every even cycle through C12 and every 3 cycles thereafter until disease progression, i.e., C2, C4, C6, C8, C10, C12, C15, C18, etc.)

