### 6.3.10 Additional Cycles

Patients will continue with the study treatment until one or more of the discontinuation criteria are met ([Section 5.8.1](#)).

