## Protocol Version 2.0 (07 Oct 2021)

This amendment (Version 2.0) updates and supersedes Protocol THE630-21-101 Version 1.0 dated 02 Sep 2021, as follows:

- Exclusion criterion #12 was modified to align more closely with FDA guidance ([Cancer Clinical Trial Eligibility Criteria: Patients with HIV, Hepatitis B Virus, or Hepatitis C Virus Infections, Guidance for Industry 2020](#)). The following text was added: “Risk of HBV reactivation should be considered in all patients and the need for anti-HBV prophylaxis should be carefully assessed. Patients with chronic HBV infection with history of active disease who meet the criteria for anti HBV therapy should be on a suppressive antiviral therapy to be eligible for enrollment. Patients who are HCV Ab positive but HCV RNA negative due to prior treatment or natural resolution are eligible. Patients on concurrent HCV treatment at the time of enrollment are allowed if HCV RNA negative.”
- Sections [5.6](#), [5.6.1](#), [5.7.2](#), [8.2](#), [8.2.2](#), [Table 1](#) footnotes 15, 16; [Table 4](#): To conform language, “drug-related” was removed as a descriptor of AEs and replaced with “AEs for which relationship to THE-630 cannot be ruled out.”
- Section [8.2.2](#): Text was amended to make the AE causality definition of “related” more explicitly consistent with the definition of a DLT. The text was updated to clarify that a causality of “related” should be assigned for all AEs for which a relationship to THE-630 cannot be clearly and incontrovertibly ruled out.
- Sections [5.8.1](#), [6.3.10](#): Removed text related to the option of continued treatment despite objective progression if the patient is continuing to experience clinical benefit in the opinion of the Investigator.
- Synopsis was updated to reflect all applicable changes.

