4.15.1 Adverse Events

A treatment-emergent adverse event (TEAE) is defined as:

- Any AE that has an onset on or after the first dose of study drug and before last dose + 30 days
- Any pre-existing AE or medical history finding that has worsened in severity on or after the first dose of study drug

A post-treatment AE is Any AE that has an onset greater than 30 days after last dose of study drug.

If an AE has missing relationship it is assumed to be related to the study drug for analysis purposes.

If a toxicity grade is missing, then the toxicity grade will be reported as missing.

The following tables will be presented for AEs:

- Overall incidence and number of TEAE, TEAEs \geq Grade 3, Treatment-Related TEAEs, Treatment-Related TEAEs \geq Grade 3, Serious Treatment Emergent Adverse Events (Treatment-Emergent SAEs), Serious Treatment-Related TEAEs (Treatment Emergent,

QMD Ref: CCI	Governing QMD: CCI
Confidentiality Statement	
CCI	

CCI		Sponsor: Theseus Pharmaceuticals, Inc.	
CCI		Protocol Number: THE630-21-101	
STATISTICAL ANALYSIS PLAN. PHASE 2-3-4			

Treatment-Related SAEs), TEAEs leading to Study Drug discontinuation, TEAEs leading to interruption of study drug, TEAEs leading to dose reduction of study drug and Fatal TEAEs.

- TEAEs by system organ class and preferred term, incidence and number of events.
- Treatment related TEAE by system organ class and preferred term, incidence and number of events.
- TEAEs \geq Grade 3 by system organ class and preferred term, incidence and number of events.
- Treatment-related TEAEs \geq Grade 3 by system organ class and preferred term, incidence and number of events.
- Serious TEAE by system organ class and preferred term, incidence and number of events.
- Serious Treatment related TEAE by system organ class and preferred term, incidence and number of events.
- TEAEs Leading to Discontinuation of Study Drug b system organ class and preferred term
- TEAEs Leading to Interruption of Study Drug by system organ class and preferred term, incidence and number of events.
- TEAEs Leading to dose reduction of Study Drug by system organ class and preferred term, incidence and number of events.
- TEAE by system organ class, preferred term and maximum toxicity, incidence.
- Treatment-Related TEAE by system organ class, preferred term and maximum toxicity, incidence.
- Fatal TEAEs by system organ class and preferred term, incidence

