10.3 BOR-confirmation of CR and PR required

BOR is calculated based on the overall visit responses obtained up until objective disease progression (i.e., RECIST response = PD). In the absence of objective disease progression, the BOR is determined using visit responses up until the last evaluable overall visit response.

CR : Overall visit response of CR confirmed at least 4 weeks later by another overall visit response of CR

PR : Overall visit response of PR confirmed at least 4 weeks later by another overall visit response of at least PR (i.e., CR/PR)

SD (≥ 6 weeks): Stable disease recorded at least 6 weeks after the date of first dose (with no prior evidence of progression)

PD: Progression in the absence of CR/PR or SD

NE: Not evaluable.

Overall response first time point	Overall response subsequent time point	Best overall response
CR	CR	CR (if subsequent time point ≥ 4 weeks after first time point)
CR	PR	SD, PD or PR ^a
CR	SD	SD-provided minimum criteria for SD duration are met. Otherwise, PD
CR	PD	SD-provided minimum criteria for SD duration are met. Otherwise, PD
CR	NE	SD-provided minimum criteria for SD duration are met. Otherwise, NE

QMD Ref: CCI	Governing QMD: CCI
Confidentiality Statement	
CCI	

CCI		Sponsor: Theseus Pharmaceuticals, Inc.	
CCI		Protocol Number: THE630-21-101	
STATISTICAL ANALYSIS PLAN. PHASE 2-3-4			

PR	CR	PR
PR	PR	PR (if subsequent time point \geq 4 weeks after first time point)
PR	SD	SD -provided minimum criteria for SD duration are met. Otherwise, PD
PR	PD	SD-provided minimum criteria for SD duration are met. Otherwise, PD
PR	NE	SD-provided minimum criteria for SD duration are met. Otherwise, NE
NE	NE	NE

^aIf a CR is truly met at first time point, then any disease seen at a subsequent time point, even disease meeting PR criteria relative to baseline, makes the disease PD at that point (since disease must have reappeared after CR). Best response would depend on whether minimum duration for SD was met.

Other considerations

There may be cases where a patient has one or more visits that are not evaluable (NE). These visits may fall in between evaluable visits. This should be taken into account. Thus, subsequent timepoint/visit does not literally mean next time point when NE visit may be involved.

[figure not shown]

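### Section 5.8.1 requires stopping for progression only if another therapy is needed, while the synopsis and Section 3.1 stop treatment at progression itself

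*Protocol*

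**What the plan says.** Section 3.1 of the protocol states: "Patients will continue with the study treatment until progression of disease as determined by the Investigator". Its other endpoints are unacceptable toxicity, death and withdrawal of consent. The synopsis, under Study Drug Administration, carries the same rule. Neither place attaches a further condition to progression.

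Section 5.8.1 is a mandatory list, introduced by "Patients will be discontinued from further study drug administration in the event of any of the following". Its only item on progression reads "Progression of disease requiring an alternate therapy, in the opinion of Investigator". The list ends with a catch-all for any other reason the investigator thinks justifies removal.

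Section 6.3.10 sets the rule for additional cycles by pointing to that list: "Patients will continue with the study treatment until one or more of the discontinuation criteria are met".

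Scheduled imaging under Section 6.3.7 is "every even cycle through C12 and every 3 cycles thereafter until disease progression". Footnote 17 to the Schedule of Events and Section 7.2.1 give the same endpoint.

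**The concern.** The two rules ask the investigator different questions. Under Section 3.1 the question is whether the disease has progressed. Section 7.2.1 ties the investigator's disease assessment to modified RECIST 1.1. Under Section 5.8.1 there is a second question, whether the progression calls for a different therapy, and no criterion is given for answering it. A patient with PD who feels well can meet the first test and not the second.

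Two things are at stake. The first is patient protection: dosing with a first-in-human drug could continue after PD with no further scheduled on-treatment scans, only imaging judged clinically indicated. The second is consistency across sites: for such a patient, every summary that depends on the date of last dose would reflect which sentence the site applied.

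**Working it through.** The protocol states no figure to reproduce here. The check compares the current texts and then traces what depends on the date of last dose.

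**1. The rules applied to one patient: PD by modified RECIST, clinically well, not judged to need another therapy**

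| Place | Trigger for stopping | Must this patient stop? |
|---|---|---|
| Synopsis, Study Drug Administration | Progression as determined by the investigator | Yes |
| Section 3.1 | Same | Yes |
| Section 5.8.1 | Progression that also calls for an alternate therapy | No; the catch-all permits a stop but does not require one |
| Section 6.3.10 | Whatever Section 5.8.1 lists | No, by reference |

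The two pairs give different answers, and no order of precedence is stated.

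**2. What the rest of the protocol assumes**

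- Scheduled scans end at progression (Sections 6.3.7 and 7.2.1).
- The at-progression blood sample and optional tissue sample are placed in the End of Treatment visit (Section 6.3.11).
- The closing paragraph of Section 5.8.1 provides for extra tumor assessments in patients who stop for some reason other than documented PD. It treats plain PD as a stopping reason, without the condition in the list above it.
- As a record of intent only, the Version 2.0 entry in Appendix 6 covers Sections 5.8.1 and 6.3.10 and says: "Removed text related to the option of continued treatment despite objective progression". The inconsistency does not rest on this log; it lies between current sections.

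All of this fits Section 3.1. None of it fits continued dosing after PD.

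**3. Timing relative to the DLT window**

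- First scheduled on-treatment scan: Cycle 2 Day 28 = 28 + 28 = study day 56.
- With the ±3-day window: 56 − 3 = day 53 to 56 + 3 = day 59.
- DLT window: the first 28 days (Sections 5.4 and 5.5).
- Gap: 53 − 28 = 25 days to 59 − 28 = 31 days.

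PD found on a scheduled scan therefore falls after the DLT window has closed.

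**4. Outputs that move with the date of last dose**

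- Duration of exposure (SAP 4.2.10) = date of last dose − date of first dose + 1. Each calendar day by which the last dose moves later adds 1 day.
- Cumulative dose (SAP 4.2.10) sums the doses taken, so every dose after PD adds to it.
- Treatment-emergent AEs (SAP 4.15.1): "Any AE that has an onset on or after the first dose of study drug and before last dose + 30 days". The cut-off moves 1 day per day.
- The swimmer's plot of treatment duration (SAP 4.13.1) lengthens accordingly.

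**5. Outputs that do not move**

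- Best overall response (SAP 10.3): "BOR is calculated based on the overall visit responses obtained up until objective disease progression". ORR and DCR are built on the same confirmed responses.
- CBR at 16 weeks (SAP 4.2.14.3) already counts a patient with PD by that assessment as having no benefit.
- DLTs and the MTD, by step 3.

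**The case against.** The best defence is that the texts can be read together. Section 3.1 ends treatment at progression, and Section 5.8.1 adds circumstances that also compel a stop. Section 5.8.1 never says that dosing may continue after PD, and a site that stops at PD complies everywhere. Its closing paragraph treats documented PD as a stopping reason, and the Version 2.0 log shows that treatment beyond progression was meant to go. Version 1.0 is not available, so it cannot be said whether the qualifier is a leftover or deliberate. Section 3.1 does not itself mention RECIST. Nothing shows that site practice differed. Exposure and the AE window are meant to follow actual dosing, so they would record it correctly. The trial has been terminated.

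Much of this stands, and it keeps the point small. The protocol does not openly permit treatment beyond PD, divergence between sites is a possibility and not an observation, and the analysis definitions are not at fault. It does not remove the conflict. Stopping at PD satisfies all the texts, but a site working from Sections 5.8.1 and 6.3.10 could continue without breaching either. The closing paragraph of 5.8.1 is evidence of the inconsistency within that section and does not cure it. Although Section 3.1 does not name RECIST, modified RECIST 1.1 is the only standard the protocol gives for the investigator's assessment of disease.

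**Conclusion.** The concern holds as a minor inconsistency in the stopping rule. For a well patient with PD, current text supports both stopping and continuing, and neither rule is given precedence.

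No effect size is claimed. The documents do not report how many patients, if any, were dosed after PD. The ceiling is the 32 enrolled before enrollment stopped (SAP Section 1), and Phase 2 will not start. The outputs affected are descriptive; the response rates and the dose-finding results are unchanged.

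The conclusion assumes that progression as determined by the investigator means PD by modified RECIST 1.1, following Section 7.2.1. It also assumes that the Section 5.8.1 catch-all is permissive, as its wording indicates.

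**What to change.** In Section 5.8.1, replace the progression item with the Section 3.1 criterion, progression as determined by the investigator, and delete the condition about needing an alternate therapy. Section 6.3.10 then follows by reference, and the four places agree with each other and with the intent recorded for Version 2.0. A parenthetical reference to modified RECIST 1.1 would be consistent with Section 7.2.1; if it is added, the same words should go into Section 3.1 and the synopsis so that no new difference arises.

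The cost is one bullet, by amendment or clarification letter. The SAP, the imaging schedule and the intra-patient escalation rules in Section 5.6.1 need no change. The downside is that investigators can no longer keep a clinically well patient with PD on drug, a discretion that Version 2.0 set out to remove.

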### **5.8.2 Patients 'Lost to Follow-up' Prior to Last Scheduled Visit**

At least 3 documented attempts must be made to contact any patient lost to follow-up at any time point prior to the last scheduled contact (office visit or telephone contact). One of these documented attempts must include a written communication sent to the patient's last known address via courier or mail (with an acknowledgement of receipt request) asking that they return any unused study drug and return to the site for final safety evaluations.

## **5.9 Treatment Supply**

### **5.9.1 Blinding**

The study will not be blinded.

### **5.9.2 Formulation, Packaging, and Labeling**

THE-630 drug product will be supplied as 1 mg, 3 mg, 12 mg and 20 mg hard gelatin capsules containing a formulated blend of excipients and THE-630 HCl. Higher strengths of capsules and/or formulated tablets will be introduced depending on the safety, PK, and biological activity of THE-630. The drug product is manufactured in accordance with cGMP. THE-630 drug product will be supplied in white high-density polyethylene (HDPE) bottles with child-resistant caps with liner. Bottle labels will bear the appropriate label text as required by governing regulatory agencies. At

a minimum, such text will include product name, product strength, number of capsules or tablets, and lot number.

### **5.9.2.1 Storage**

The Investigator has overall responsibility for ensuring that study drug is stored in a secure, limited-access location. Limited responsibility may be delegated to the pharmacy or member of the study team, but this delegation must be documented. Study drug is distributed by the pharmacy or nominated member of the study team.

Study drug will be stored in accordance with the labeled storage conditions. Temperature monitoring is required at the storage location to ensure that the study drug is maintained within an established temperature range. The Investigator is responsible for ensuring that the temperature is monitored throughout the duration of the study and that records are maintained; the temperature should be monitored continuously by using either an in-house system, a mechanical recording device, such as a calibrated chart recorder, or by manual means, such that both minimum and maximum thermometric values over a specific time period can be recorded and retrieved as required. Such a device (i.e., certified Min/Max Thermometer) would require manual resetting upon each recording. The Sponsor must be notified upon discovery of any excursion from the established range. Temperature excursions will require site investigation as to cause and remediation. The Sponsor will determine the ultimate impact of excursions on the study drug and will provide supportive documentation as necessary. Under no circumstances should product be dispensed to patients until the impact is determined and product is deemed appropriate for use by Sponsor.

## **5.10 Study Drug Quality Complaints**

For information on defining and reporting study drug quality complaints, please refer to the Pharmacy Manual.

## **5.11 Study Drug Accountability**

The Investigator or designee will acknowledge receipt of the study drug, documenting shipment content and condition. Accurate records of all study drug dispensed, used, returned, and/or destroyed must be maintained as detailed further in this section.

The Investigator has overall responsibility for administering/dispensing study drug. Where permissible, tasks may be delegated to a qualified designee (e.g., a pharmacist) who is adequately trained in the protocol and who works under the direct supervision of the Investigator. This delegation must be documented in the applicable study delegation of authority form.

The Investigator or his/her designee will dispense the study drug only to patients included in this study following the procedures set out in the study protocol. Each patient will be given only the study drug carrying his/her treatment assignment. All dispensing will be documented on the study drug source document records. The Investigator is responsible for assuring the retrieval of all study supplies from patients.

Direct shipment of study drug to patient's home or local pharmacy may be allowed with prior authorization from the Sponsor provided that chain of custody is maintained and documented and local policies and regulations are followed.

The Sponsor or its representatives must be permitted access to review the study drug supplies storage, distribution procedures, and records. Based on entries in the study drug accountability forms, it must be possible to reconcile study drug delivered with those used and returned. All study drug must be accounted for and all discrepancies investigated and documented to the Sponsor's satisfaction.

No study drug stock or returned inventory from a Theseus-sponsored study may be removed from the site where originally shipped without prior knowledge and consent by the Sponsor or designee. If such transfer is authorized by the Sponsor or designee, all applicable local, state, and national laws must be adhered to for the transfer.

At the end of the study, or as instructed by the Sponsor or designee, all unused stock, patient-returned study drug, and empty/used study drug packaging may be destroyed at the site or a local facility, or returned to the Sponsor depot. All study drug must be counted and verified by clinical site personnel prior to destruction or return. Records identifying what was destroyed or returned, when, how, and by whom must be maintained with copies provided to the Sponsor. Destruction of study drug at the site or a local facility must be in accordance with local, state, and national laws, as well as investigational site pharmacy's Standard Operating Procedures (SOPs).

For unused supplies where the original supplied tamper-evident feature is verified as intact, the tamper evident feature must not be broken, and the labeled amount is to be documented in lieu of counting. Returned study drug must be packed in a tamper-evident manner to ensure product integrity. Contact the Sponsor for authorization to return any study drug prior to shipment.

